APPENDIX 6. SCHEDULE OF ASSESSMENTS49

LIST OF TABLES

Table 1 Dosing Sequences16

SYNOPSIS

Name of Sponsor/Company: BeiGene Ltd.
Investigational Product: Sitratavinib
Title of Study: A Phase 1, Open-label, Single-dose, Randomized Crossover Study to Evaluate the Relative Bioavailability of Two Different Capsule Formulations of Sitratavinib in Healthy Subjects
Protocol Identifier: BGB-Sitratavinib-101
Phase of Development: Relative Bioavailability Study
Number of Subjects: Up to 26 healthy subjects in total (include ≥ 16 Asian subjects)
Study Centers: 1 center in Australia
Study Objectives: Primary: 
To investigate the relative bioavailability and pharmacokinetics (PK) of sitratavinib free base and malate salt capsule formulations following oral administration in healthy subjects. Secondary: 
To assess the safety and tolerability of single-dose free base and malate salt capsule formulations of sitratavinib in healthy subjects.
Study Endpoints: Primary: 
The primary PK parameters will include area under the plasma concentration-time curve (AUC) from time zero to infinity ($AUC_{0-\infty}$), AUC from time zero to the last quantifiable concentration (AUC_{0-t}) and maximum observed plasma concentration (C_{max}). Other PK variables will be assessed for description purposes. Secondary: 
Safety endpoints for this study include adverse events, clinical laboratory evaluations, 12-lead electrocardiograms, vital sign measurements, and physical examinations.
Study design: 
This will be a Phase 1, open-label study using a 2-period crossover design to compare the bioavailability and PK of the free base formulation at 120 mg and the malate salt capsule formulation at 100 mg after a single oral administration to healthy male subjects. Subjects will be randomized into 2 dosing sequences and will participate in 2 dosing periods as shown below. The minimum washout period between dose administrations will be 14 days.
 
Potential subjects will be screened to assess their eligibility to enter the study within 28 days prior to the first dose administration. In Periods 1 and 2, subjects will be admitted into the Clinical Research Unit (CRU) on Day -1 and will stay in the CRU until discharge on Day 4. In each period, subjects will attend a nonresidential visit on Day 8 for PK (168 hours postdose) sampling. A poststudy assessment will be performed on Day 8 of Period 2. Subjects will receive a Follow-up phone call on Days 13 to 15 of Period 2.

Dosing sequence	Period 1	Washout (minimum)	Period 2
1 N=13	120 mg sitravatinib free base capsule	14 days	100 mg sitravatinib malate salt capsule
2 N=13	100 mg sitravatinib malate salt capsule	14 days	120 mg sitravatinib free base capsule

N: number of subjects

Diagnosis and main criteria for inclusion:

Healthy male subjects aged between 18 and 55 years (inclusive) with a body mass index between 18.0 and 32.0 kg/m² (inclusive).

Investigational products, dose, and mode of administration:

120 mg sitravatinib free base formulation given orally as 3 × 40-mg capsules after an overnight fast period.

100 mg sitravatinib malate salt capsule formulation given orally as 2 × 50-mg capsules after an overnight fast period.

Duration of subject participation in the study:

Planned Screening duration: approximately 4 weeks.

Planned study duration (Screening to Follow-up phone call): up to approximately 8 weeks.

Blood Sampling Timepoints

Blood samples for PK analysis will be collected at the following time points: predose (within 30 minutes before administration of sitravatinib), 0.5, 1, 2, 4, 6, 8, 12, 24, 48, 72, and 168 hours after dose in each period. A total of 12 samples will be collected from each subject in one period.

Statistical methods:

Pharmacokinetics

The primary PK parameters are AUC_{0-∞}, AUC_{0-t}, and C_{max} for sitravatinib. All other PK parameters will not be subject to inferential statistical analysis.

For the analysis of relative bioavailability between sitravatinib malate salt (test) and sitravatinib free base (reference), log-transformed primary PK parameters (AUC_{0-∞}, AUC_{0-t}, and C_{max}) for sitravatinib will be analyzed by using a mixed effect model. This model will include formulation, period, and sequence as fixed effects, and subject as a random effect.

For each primary PK parameter, a point estimate and its associated 90% confidence interval (CI) will be constructed for the difference between test and reference capsules and this difference and its 90% CI will be exponentiated to obtain the estimate of the ratio of geometric least squares means and its 90% CI.

Safety

Safety parameters will be listed and summarized using descriptive statistics, as applicable. No formal statistical analysis of safety data is planned.

LIST OF ABBREVIATIONS AND TERMS

Abbreviation	Definition
ADL	activities of daily living
AE	adverse event
AUC	area under the plasma concentration-time curve
AUC _{0-∞}	area under the plasma concentration-time curve from time zero to infinity
AUC _{0-t}	area under the plasma concentration-time curve from time zero to the last quantifiable concentration
CFR	Code of Federal Regulations
CI	confidence interval
CIT	checkpoint inhibitor therapy
CL/F	apparent total plasma clearance
C _{max}	maximum observed plasma concentration
COVID-19	Corona Virus Disease-2019
CRO	Contract Research Organization
CRU	Clinical Research Unit
CV%	coefficient of variation
CYP	cytochrome P450
ECG	electrocardiogram
eCRF	electronic Case Report Form
EDC	electronic data capture
FDA	Food and Drug Administration
GCP	Good Clinical Practice
IB	Investigator's Brochure
ICF	Informed Consent Form
ICH	International Council for/Conference on Harmonisation
IMP	investigational medicinal product
IRB	Institutional Review Board
IV	intravenous
MTD	maximum tolerated dose
NCI CTCAE	National Cancer Institute Common Terminology Criteria for Adverse Events
NSCLC	non-small cell lung cancer
PK	pharmacokinetic(s)

QD	once daily
QTcF	QT interval corrected for heart rate using Fridericia's method
RP2D	recommended Phase 2 dose
SAE	serious adverse event
SUSAR	suspected unexpected serious adverse reaction
$t_{1/2}$	apparent plasma terminal elimination half-life
T_{max}	time of the maximum observed plasma concentration
V_z/F	apparent volume of distribution

1. INTRODUCTION

Refer to the Investigator's Brochure (IB)¹ for detailed information concerning the available pharmacology, toxicology, drug metabolism, clinical studies, and adverse event (AE) profile of the investigational medicinal product (IMP).

1.1. Overview

Sitravatinib (MGCD516) is an orally available, potent small-molecule inhibitor of a closely related spectrum of tyrosine kinases. This subset of tyrosine kinases is involved in a number of processes implicated in human cancer, including regulation of tumor growth and cell survival pathways, tumor invasion and metastatic progression, as well as tumor angiogenesis. Antitumor activity of sitravatinib has been observed in several human tumor xenograft models exhibiting genetic alterations in receptor tyrosine kinase targets, providing the rationale for evaluating sitravatinib monotherapy in tumors driven by these pathways in the clinical setting.

Additionally, based on its tyrosine kinase target profile, sitravatinib may modulate effects on the tumor microenvironment to overcome resistance to checkpoint inhibitors by effects on relevant immune cell populations. These effects are predicted to complement and augment the activity observed with checkpoint inhibitor therapy (CIT).

1.2. Summary of Nonclinical Studies

Sitravatinib is metabolized to 8 putative metabolites (M1 to M8) in mouse, rat, dog, monkey, and human hepatocytes and to 13 putative metabolites (M1 to M7 and M9 to M14) in vivo in dog and rat plasma samples. Studies using human liver microsomes and recombinant human cytochrome P450 (CYP) enzymes suggest that multiple enzymes (CYP1A2, CYP2A6, CYP2B6, CYP2C8, CYP2C9, CYP2D6, CYP2E1, and CYP3A4) are involved in the metabolism of sitravatinib; therefore, there is a low risk of a single CYP enzyme demonstrating a disproportionate contribution to sitravatinib metabolism.

Toxicology studies with repeated dosing of sitravatinib for 7 days and 4 weeks demonstrated no target organ changes in the dog, despite overt decreases in body weight and food consumption. In rats, however, vascular endothelial growth factor-related target organ changes were identified in the adrenal gland, Brunner's glands in the duodenum, femur and sternum (bone and bone marrow), spleen, lymph nodes, thymus, ovary, kidney (glomerulopathy, tubule necrosis, increased basophilic tubules), pancreas, and tongue. All effects in rats, except those in the kidney and pancreas, either recovered or showed partial recovery.

1.3. Summary of Clinical Experience

In clinical studies, sitravatinib was administered as a single agent in the first-in-human Study 516-001 in patients with advanced solid tumors and in combination with the PD-1 inhibitor nivolumab in patients with advanced or metastatic non-squamous non-small cell lung cancer (NSCLC) who had experienced disease progression either on or after prior treatment with a CIT (CIT-experienced) or after treatment with a platinum-based doublet chemotherapy (CIT-naïve) in Study MRTX-500.

Study 516-001 is an ongoing multicenter, Phase 1/1b clinical study characterizing the safety, pharmacokinetics (PK), metabolism, the pharmacodynamic, and clinical activity of sitravatinib in

patients with advanced solid tumors. The primary objective of the Phase 1 study was the determination of the maximum tolerated dose (MTD), while Phase 1b objectives included assessment of safety and clinical activity in patients with certain tumor types (eg, renal cell carcinoma) or with tumors characterized by certain genetic alterations. Sitravatinib monotherapy was administered orally once daily (QD) and based on the Phase 1 results, the starting dose in Phase 1b was 150 mg daily, which was subsequently changed to 120 mg during the study. Study MRTX-500 is a parallel Phase 2 study of glesatinib, sitravatinib, or mocetinostat in combination with nivolumab administered at a dose of 240 mg intravenously (IV) every 2 weeks, with sitravatinib 120 mg administered QD after this dose was confirmed safe in the lead-in portion of the study.

Study 516-006 is an Mirati sponsored, open-label, 2 parts, Phase 1 study assessing relative bioavailability and PK of a single oral dose of sitravatinib administered as free base capsules (reference formulation) and malate salt capsules (test formulation, developed by Mirati) in healthy male subjects. The primary objective is to investigate the relative bioavailability and PK of sitravatinib free base and malate salt capsule formulations following oral administration in healthy subjects. The results showed that PK exposure of 100 mg sitravatinib malate salt capsule (roller compaction) was comparable with 120mg free base capsule.

1.3.1. Safety

As of 26 June 2019, a total of 422 patients received treatment with sitravatinib. Among the 422 patients with available safety data, 377 patients (89%) experienced at least one sitravatinib-related AE.

Sitravatinib-related Grade 3 AEs reported in $\geq 5\%$ of patients were hypertension (19%), diarrhea (8%), and fatigue (6%). Sitravatinib-related Grade 4 AEs were reported in 7 patients (2%), and included lipase increased in 3 patients (1%), and febrile neutropenia, gastric ulcer perforation, hypertensive crisis, and lymphocyte count decreased in 1 patient each ($<1\%$). Sitravatinib-related Grade 5 AEs were reported in 4 patients and included cardiac arrest in 3 patients (1%) and cardiac failure in 1 patient ($<1\%$).

Among the 422 patients with available safety data, 176 patients (42%) experienced at least one treatment-emergent serious adverse event (SAE). Sitravatinib-related SAEs were reported in 61 patients (15%), and included diarrhea in 10 patients (2%), nausea and vomiting in 7 patients each (2%), hypertension in 6 patients (1%), fatigue in 5 patients (1%), pulmonary embolism in 4 patients each (1%), cardiac arrest, headache and pancreatitis in 3 patients each (1%), cardiac failure, deep vein thrombosis, ejection fraction decreased, embolism, non-cardiac chest pain, and palmar-plantar erythrodysesthesia syndrome in 2 patients each (1%), and anaphylactic reaction, anemia, cerebral vasoconstriction, clostridium difficile colitis, confusional state, dehydration, electrocardiogram QT prolonged, febrile neutropenia, gastric ulcer perforation, gastritis, hypertensive crisis, hyponatremia, hypotension, left ventricular dysfunction, lipase increased, myalgia, myocarditis, odynophagia, pericardial effusion, pneumonitis, posterior reversible encephalopathy syndrome, subarachnoid hemorrhage, syncope, tachycardia, transaminases increased, and Troponin T increased in 1 patient each ($<1\%$).

As of the data cut-off date, safety data are available for a total of 16 subjects from study 516-006. Among the 16 subjects with available safety data, three subjects experienced one AE each of dyspepsia, ear discomfort, and toothache; all were Grade 1 and none were drug-related. The

toothache led to withdrawal from study prior to dosing in dosing period 2. There were no SAEs and no deaths reported.

1.3.2. Pharmacokinetics

Pharmacokinetic evaluation in Study 516-001 shows that after single-dose administration, sitravatinib reaches peak concentration in a median time of approximately 3 to 8 hours. Exposure parameters (maximum observed plasma concentration [C_{max}] and area under the plasma concentration-time curve [AUC]) are approximately dose-proportional with single doses up to 200 mg. Median apparent plasma terminal elimination half-life ($t_{1/2}$) varied between 42 and 58 hours after oral administration.

After multiple-dose administration, drug accumulation ranged from 1.8- to 3.5-fold for C_{max} and 2.0- to 4.7-fold for AUC from time zero to 24 hours postdose (AUC_{0-24}). Steady-state C_{max} to a minimum observed plasma concentration mean ratio was 1.10 to 1.78. The steady-state PK was reached in a mean time of 11 to 15 days.

1.4. Study Rationale

In order to introduce BeiGene malate salt capsule formulation (roller compaction) into the development of sitravatinib in China, this study is conducted to compare the systemic exposure of sitravatinib between the malate salt capsule (roller compaction, manufactured by BeiGene) and the free base formulation. The primary objective of the study is to evaluate the relative bioavailability and PK of the different formulations.

The sitravatinib doses in this study are based on the results from study 516-006. To ensure comparable exposures, the free base reference dose will be 120 mg and the malate salt capsule dose will be 100 mg. The exposure ratio information should be used to guide the dose for the selected malate salt capsule formulation needed to achieve exposure comparable to the recommended Phase 2 dose (RP2D) of the free base product.

1.5. Benefit-risk Assessment

Healthy subjects in the current study will not receive any health benefit (beyond that of an assessment of their medical status) from participating in the study. The risks of participation are primarily those associated with adverse reactions to the study products, although there may also be some discomfort from the collection of blood samples and other study procedures. More information about the known and expected benefits, risks, and reasonably anticipated AEs associated with sitravatinib may be found in the IB¹.

2. OBJECTIVES AND ENDPOINTS

2.1. Objectives

The primary objective of the study is:

- To investigate the relative bioavailability and PK of sitravatinib free base and malate salt capsule formulations following oral administration in healthy subjects.

The secondary objective of the study is:

- To assess the safety and tolerability of single-dose free base and malate salt capsule formulations of sitravatinib in healthy subjects.

2.2. Endpoints

2.2.1. Primary Endpoints

The following PK parameters will be calculated separately for each of Parts 1 and 2 using noncompartmental methods, whenever possible, based on plasma sitravatinib concentrations:

- AUC from time zero to infinity ($AUC_{0-\infty}$)
- AUC from time zero to the last quantifiable concentration (AUC_{0-t})
- C_{max}
- time of the maximum observed plasma concentration (T_{max})
- $t_{1/2}$
- apparent total plasma clearance (CL/F)
- apparent volume of distribution (V_z/F).

Other PK parameters may also be reported, as appropriate. Dose-normalized PK parameters will also be derived.

2.2.2. Secondary Endpoints

The safety outcome measures for this study are as follows:

- incidence and severity of AEs
- incidence of laboratory abnormalities, based on hematology, clinical chemistry, and urinalysis test results
- 12-lead electrocardiogram parameters
- vital sign measurements
- physical examinations.

3. INVESTIGATIONAL PLAN

3.1. Overall Study Design and Plan

This will be a Phase 1, open-label study using a 2-period crossover design to compare the bioavailability and PK of the free base formulation at 120 mg and the malate salt capsule formulation at 100 mg after a single oral administration to healthy male subjects. Subjects will be randomized into 2 sequences and will participate in 2 dosing periods (Table 1). The minimum washout period between dose administrations will be 14 days. Up to 26 subjects (include ≥ 16 Asian subjects) will be enrolled to guarantee that at least 24 subjects complete the study.

Table 1 Dosing Sequences

Dosing sequence	Period 1	Washout (minimum)	Period 2
1 N=13	120 mg sitravatinib free base capsule	14 days	100 mg sitravatinib malate salt capsule
2 N=13	100 mg sitravatinib malate salt capsule	14 days	120 mg sitravatinib free base capsule

N: number of subjects

Potential subjects will be screened to assess their eligibility to enter the study within 28 days prior to the first dose administration. In Periods 1 and 2, subjects will be admitted into the Clinical Research Unit (CRU) on Day -1 and will stay in the CRU until discharge on Day 4. In each period, subjects will attend a nonresidential visit on Day 8 for PK (168 hours postdose) sampling. Subjects will receive a Follow-up phone call on Days 13 to 15 of Period 2. A Schedule of Assessments is presented in Appendix 6.

The total duration of study participation for each subject (from Screening through Follow-up phone call) is anticipated to be up to approximately 8 weeks.

The start of the study is defined as the date the first enrolled subject signs an Informed Consent Form (ICF). The point of enrollment occurs at the time of randomization number allocation. The end of the study is defined as the date of the last subject's last assessment (scheduled or unscheduled).

3.2. Discussion of Study Design

This study has been designed according to the Food and Drug Administration (FDA) Guidance for bioavailability and bioequivalence studies². A crossover design was selected in order to assess the PK of sitravatinib after administration of sitravatinib free base and malate salt capsule. The crossover design allows for the smallest number of subjects to be used in the comparison of formulations.

A minimum 14-day washout between periods is considered adequate to ensure elimination of study drug prior to dosing in the subsequent period. The sample size is typical for this type of study and is considered adequate to meet the study objectives.

Conducting the study in healthy subjects mitigates the potential confounding effects of the disease state and concomitant medications.

3.3. Selection of Doses in the Study

The PK profile of single-agent sitravatinib was evaluated in Study 516-001 after single and repeated dose administration in patients with advanced solid tumors. Study 516-001 evaluated sitravatinib dose levels between 10 and 200 mg administered QD. Exposure parameters (C_{max} and AUC) were approximately dose proportional with single doses up to 200 mg. The MTD was identified as 150-mg QD, and based on long-term tolerability observed in patients enrolled into Study 516-001 treated with 120- or 150-mg QD, the Sponsor selected 120-mg QD as the current RP2D, using the sitravatinib free base capsule formulation.

The sitravatinib doses in this study are based on the results from study 516-006, in which the PK exposure of 100 mg sitravatinib malate salt capsule (roller compaction, manufactured by Mirati) is comparable with 120 mg sitravatinib free base capsule. In this study, the free base reference dose will be 120 mg and the malate salt capsule (roller compaction, manufactured by BeiGene) test dose will be 100 mg to compare their systemic exposure.

Doses of 100 or 120 mg sitravatinib proposed in this study are considered safe and appropriate for the evaluation of sitravatinib PK profiles in healthy subjects. Also, see additional dose rationale provided in Section [1.4](#).

4. SELECTION OF STUDY POPULATION

4.1. Inclusion Criteria

Subjects must satisfy all of the following criteria at the Screening visit unless otherwise stated:

1. Males, between 18 and 55 years of age, inclusive.
2. Body mass index between 18.0 and 32.0 kg/m², inclusive.
3. Subjects of first-generation or second-generation Asian descent enrolled in this study will be defined as:

A subject of first-generation Asian descent for this study is defined as an individual who was born to biological parents of Asian descent in any East/Southeast Asian countries and relocated, or whose biological parents were born in any East/Southeast Asian countries/territories (such as China, Korea, Taiwan, Hong Kong, Mongolia, Cambodia, Vietnam, Thailand, Indonesia, Malaysia, Philippines, Myanmar, Laos, Singapore, etc.).

A subject of second-generation Asian descent for this study is defined as an individual whose 4 biological grandparents were born in any East/Southeast Asian countries and relocated, or whose biological parents were born in any East/Southeast Asian countries/territories (such as China, Korea, Taiwan, Hong Kong, Mongolia, Cambodia, Vietnam, Thailand, Indonesia, Malaysia, Philippines, Myanmar, Laos, Singapore, etc.).

Subjects of non-Asian descent enrolled in this study will be defined as an individual whose biological parents and 4 biological grandparents were not born in any East/Southeast Asian countries and relocated, or whose biological parents were born in any East/Southeast Asian countries/territories (such as China, Korea, Taiwan, Hong Kong, Mongolia, Cambodia, Vietnam, Thailand, Indonesia, Malaysia, Philippines, Myanmar, Laos, Singapore, etc.).

4. In good health, determined by no clinically significant findings from medical history, physical examination, 12-lead ECG, vital sign measurements, and clinical laboratory evaluations at Screening and/or Check-in as assessed by the Investigator (or designee).
5. A non-vasectomized male subject when sexually active with female partners of childbearing potential must agree to use a male condom or abstain from sexual intercourse during the study until 6 months after the last dose of study drug (this also applies to male subjects with pregnant partners). A vasectomized male subject will be surgically sterile for at least 90 days prior to study start, with documented azoospermia. A male who has been vasectomized less than 90 days prior to study start must follow the same restrictions as a non-vasectomized male. Contraception is further detailed in [Appendix 4](#).
6. Agree to not donate sperm for 6 months after last dose.
7. Are able to swallow multiple capsules.
8. Able to comprehend and willing to sign an ICF and to abide by the study restrictions.

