7. PREGNANCY REPORTING

If the partner of a male subject becomes pregnant within 6 months after the completion of the last dose of study drug, a pregnancy report form should be completed and expeditiously submitted to the sponsor to facilitate outcome follow-up. Information on the status of the mother and child will be forwarded to the sponsor. Generally, follow-up will be 1 year following the delivery date. Any premature termination of the pregnancy will be reported.

While pregnancy itself is not considered to be an AE or SAE, any pregnancy complication or elective termination of a pregnancy for medical reasons will be recorded as an AE or SAE.

An abortion, whether accidental, therapeutic, or spontaneous, should be always reported as an SAE. Similarly, any congenital anomaly/birth defect in a child born to a subject exposed to the study drug should be recorded and reported as an SAE.

8. EXPEDITED REPORTING TO HEALTH AUTHORITIES, INVESTIGATORS, INSTITUTIONAL REVIEW BOARDS, AND ETHICS COMMITTEES

The sponsor will promptly assess all SAEs against cumulative study drug experience to identify and expeditiously communicate new safety findings to regulatory authorities, investigators, and IRBs based on applicable legislation.

To determine the reporting requirements for individual SAEs, the sponsor will assess the expectedness of the SAEs using the following reference documents:

- [Sitravatinib Investigator's Brochure](#)

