APPENDIX 4. CONTRACEPTION GUIDANCE

Definitions

Fertile male: a male that is considered fertile after puberty.

Sterile male: permanently sterile male via vasectomy with documented azoospermia.

Contraception Guidance

Male Subjects

Sexually active males who are non-vasectomized when sexually active with female partners of childbearing potential and males who have had a vasectomy within 90 days prior to study start must agree to use a male condom or abstain from sexual intercourse during the study from Period 1 Check-in until 6 months after the last dose of study drug. Sexually active males who have had a vasectomy and are surgically sterile for greater than 90 days prior to study start, with documented azoospermia, will not be required to use a male condom or abstain from sexual intercourse during the study from Period 1 Check-in until 6 months after the last dose of study drug. The use of a condom applies to sexual intercourse with female partners of childbearing potential and female partners who are pregnant and breastfeeding.

Sexual Abstinence and Same-sex Relationships

For subjects who practice true abstinence, subjects must be abstinent for at least 6 months prior to Screening and must agree to remain abstinent from the time of signing the Informed Consent Form (ICF) until 6 months after the last dose.

For subjects in same-sex relationships at the time of signing the ICF, there must be an agreement to refrain from engaging in a heterosexual relationship from the time of signing the ICF until 6 months after the last dose.

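### The sperm-donation restriction starts only at the last dose, so men who take both doses have no donation limit between them

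*Protocol*

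**What the plan says.** Protocol Section 4.1 sets two separate reproductive precautions.

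- **Sperm donation (criterion 6):** "Agree to not donate sperm for 6 months after last dose". No start before the last dose is given.
- **Condom or abstinence (criterion 5):** this duty falls on a sexually active, non-vasectomized man whose female partners could become pregnant; he "must agree to use a male condom or abstain from sexual intercourse during the study until 6 months after the last dose of study drug". Appendix 4 states the start of this duty: "during the study from Period 1 Check-in until 6 months after the last dose of study drug".

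Nothing else in the two documents restricts sperm donation. Section 6.5 deals with blood, plasma and platelets. Appendix 4 deals with condoms, abstinence and same-sex relationships. Pregnancy reporting (Appendix 1, Section 7) also counts from the last dose: "If the partner of a male subject becomes pregnant within 6 months after the completion of the last dose of study drug".

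Under Section 3.1 each subject is planned to take two single doses with a washout of at least 14 days. In each period he enters the CRU on Day -1 and "will stay in the CRU until discharge on Day 4"; later, "subjects will attend a nonresidential visit on Day 8 for PK (168 hours postdose) sampling".

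**The concern.** A man who takes both doses and follows criterion 6 to the letter has agreed to no donation limit from his first dose until his second. The sponsor judged six months after dosing to need this precaution, yet the days directly after the Period 1 dose are outside it, and the documents give no reason.

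The two duties do not contradict each other, and a subject can meet both. The point is that the donation window opens too late. The condom duty cannot stand in for it, because condom use does not prevent donation. The pregnancy-reporting rule concerns the partner of a subject and is tied to the last dose, so it does not close the gap either.

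What is at stake is a third party's possible exposure, not any result of the trial.

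**Working it through.** The plan states no figure to reproduce. The check compares the two windows and then measures the uncovered interval.

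**Windows side by side, for a subject who takes both doses**

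| Interval | Condom/abstinence (criterion 5, Appendix 4) | Sperm donation (criterion 6) |
|---|---|---|
| Period 1 Check-in to Period 1 dose | Covered | Not covered |
| Period 1 dose to Period 2 dose | Covered | Not covered |
| Period 2 dose to 6 months later | Covered | Covered |

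A subject who stops after Period 1 has no gap after dosing, because the Period 1 dose is then his last.

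**Which dose is the last dose?** Criterion 5, immediately above, names the on-study period separately and then counts six months from the last dose. There the phrase means the final dose, and Appendix 4 uses it the same way. Other restrictions, such as those on grapefruit, alcohol, tobacco, exercise and blood donation, also state when they begin. Criterion 6 departs from that pattern.

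**Inputs**

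- Minimum interval between doses: 14 days (Section 3.1).
- Discharge on Day 4, which is 72 h after dosing (Appendix 6).
- Check-in on Day -1 of Period 2. There is no Day 0 (SAP Section 5.1.2), so this is the day before the Period 2 dose.
- Median terminal half-life in Study 516-001, in patients with advanced solid tumors, "varied between 42 and 58 hours after oral administration" (Section 1.3.2).

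**Length of the gap at minimum washout**

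- Period 1 dose: Day 1, 0 h.
- Period 2 dose: 14 × 24 = 336 h, on Period 1 Day 15.
- Period 2 Check-in: Period 1 Day 14, about 13 × 24 = 312 h.
- Time outside the CRU: (312 − 72)/24 = 10 days.

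**Drug still present during those 10 days**

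Half-lives elapsed = hours since dose ÷ half-life. Fraction remaining = 0.5 raised to that number, assuming simple exponential decay.

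| Time after Period 1 dose | Half-lives elapsed (58 h to 42 h) | Fraction remaining (42 h to 58 h) |
|---|---|---|
| 72 h (discharge) | 72/58 = 1.2 to 72/42 = 1.7 | 31% to 42% |
| 168 h (Day 8 sample) | 168/58 = 2.9 to 168/42 = 4.0 | 6% to 13% |
| 312 h (Period 2 Check-in) | 312/58 = 5.4 to 312/42 = 7.4 | 0.6% to 2.4% |

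The outpatient sample at 168 h falls inside the unrestricted interval. These figures describe drug in plasma only and do not measure transfer in semen.

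**The case against.** The strongest counter-argument is that nobody knows during the washout whether a second dose will be given. Subjects may withdraw at any time, and Section 1.3.1 reports a withdrawal before Period 2 dosing in Study 516-006. If that happens, the Period 1 dose becomes the last dose and a donation made in the washout breaches criterion 6. Between doses, the only conduct certain to comply is not donating. This is a fair description of the logic, but it does not close the gap for a man who goes on to Period 2: his washout donation breaches nothing. A subject told to count from the last dose would also naturally think of the second one he is scheduled to receive.

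Other points stand as limits:

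- Reading the last dose as the most recent dose would close the gap. That reading is possible but less natural, given criterion 5 and Appendix 4.
- Consent pages were not available, so subjects may have been told something stricter. The finding concerns the protocol text.
- Subjects live in the CRU for the first 72 h, which includes peak exposure (median peak time about 3 to 8 h). The practical gap is nearer 10 days than 14.
- Twenty-six men is a ceiling. Vasectomized men with documented azoospermia are eligible, and subjects who stop after Period 1 are unaffected.
- No donation rate or semen-transfer data are given, and the half-lives come from patients. The hazard cannot be quantified and may be very small.

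It is also fair to call this a drafting omission: nothing suggests the sponsor meant to allow donation between doses.

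**Conclusion.** The concern holds. For each subject who takes both doses, criterion 6 as written leaves at least 14 days after the first dose without a donation limit, about 10 of them outside the CRU at minimum washout. A longer washout lengthens the gap. On the patient half-lives, drug is still present for much of that time.

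This is a minor third-party safety gap that should be corrected because the remedy is almost free. Confidence is medium. The conclusion rests on reading the last dose as the final dose and on the protocol text alone. The size of any harm cannot be stated, and no pharmacokinetic or statistical conclusion is affected.

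**What to change.** Give criterion 6 the window that Appendix 4 already uses, so that subjects agree not to donate sperm "during the study from Period 1 Check-in until 6 months after the last dose of study drug". Add one sentence to Appendix 4 with the same rule, and check that the consent form gives the same interval.

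The cost is one phrase in criterion 6, one sentence in Appendix 4 and the consent check. No visit, procedure or data item is added, and the SAP does not change.
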